14. ADVERSE EVENTS, ADVERSE DEVICE EFFECTS AND DEVICE DEFICIENCIES

Throughout the course of the proposed study, all efforts will be made to remain alert to possible adverse reactions or untoward findings. If adverse reactions occur, the first concern will be the safety and welfare of the subject and appropriate medical intervention will be made. Any adverse reactions or complications observed by the investigator or reported by the subjects will be recorded in the appropriate section of the subject's Case Report Form.

Any serious adverse event and/or severe, sight-threatening adverse event will be promptly communicated by telephone to CRO, the Medical Monitor, and to the IRB. These reports must be confirmed in writing within five (5) working days of the occurrence.

Any subjects who are terminated from the study due to adverse events will be followed until their medical outcome is determined and the Investigator will provide written reports to CRO as appropriate.

Definition and Classification of Adverse Events:

Definition and classification of adverse reactions in this study will follow the requirements outlined in US FDA/CDRH Guidance Document for Class II Daily Wear Contact Lenses. (1994) Parts 3 and 4 Clinical Section -Appendix B and C page 45-96, and ISO 11980:2009

Ophthalmic optics -- Contact lenses and contact lens care products -- Guidance for clinical investigations.

Adverse Reaction: Considered to include but not limited to a hazardous, sight threatening condition such as corneal ulcers, severe corneal abrasion > 2mm in diameter, iritis, other ocular infections or inflammations, corneal scarring or permanent loss of vision

Slit Lam Finding (SLF) Requiring Treatment: Any slit lamp finding in any examination, scheduled or unscheduled that requires treatment including temporary discontinuation of lens wear, to maintain normal ocular health. This does not include SLFs that are corrected by refitting of lenses without discontinuation of wear or by retraining patients in proper lens care.

Symptom, Problem or Complaint (SPC) Requiring Treatment: Any symptom, problem or complaint that requires treatment including temporary discontinuation of lens wear, to maintain normal ocular health. This does not include SPCs that are corrected by refitting of lenses without discontinuation of wear or by retraining patients in proper lens care.

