Significant but non-serious adverse events	Significant but non-serious AEs should include, but not be limited to: 
 — peripheral non-progressive non-infectious ulcers; — all symptomatic corneal infiltrative events; — all cases of corneal staining greater than or equal to grade 3; — a temporary loss of two or more lines of best corrected visual acuity (for greater than or equal to 2 weeks); — cases greater than or equal to grade 2 neovascularization; — any ocular event that necessitates temporary lens discontinuation of greater than or equal to 2 weeks; — lens adhesion or lens binding to the cornea; — significantly distorted corneal topography (significant distortion of keratometry mires or aberrant findings in corneal topography); — any ocular AE that requires the practitioner's intervention, including medication (not including minimal lubrication). 	Notify sponsor as soon as possible, within 5 working days ; IRB and FDA reporting as per requirements
Unanticipated Adverse Device Effect	Unanticipated adverse device effect means any serious adverse effect on health or safety or any life-threatening problem or death caused by, or associated with, a device, if that effect, problem, or death was not previously identified in nature, severity, or degree of incidence in the investigational plan or application (including a supplementary plan or application), or any other unanticipated serious problem associated with a device that relates to the rights, safety, or welfare of subjects.	Notify sponsor immediately ; IRB and FDA reporting as per requirements

Procedures for Handling Adverse Events:

Treatment of an adverse event will depend on its nature and severity. Based on the clinical judgment of the investigator, the subject may be referred to a pre-designated ophthalmologist for treatment. The investigator will attempt to determine whether the reaction is related to the contact lenses or a result of other factors. An Adverse Event Form will be completed for each adverse event. If both eyes are involved, each eye will be counted as one adverse event and Adverse Event information will be completed *for each eye*. Whenever possible, the adverse event will be photo-documented.

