In any case of a corneal infiltrate with overlying full thickness epithelial loss, or in any case of presumed corneal keratitis a culture will be taken in accordance with the procedures identified in *Premarket Notification [510(k)] Guidance Document for Class II Daily Wear Contact Lenses*, which may be referenced in Appendix 4 of this protocol. The investigator will immediately (same business day) report cases that require culturing to the Medical Monitor and CRO.

Expenses incurred for medical treatment as part of study participation will be paid by the sponsor (bills and prescription receipts kept). The subject must be followed until resolution and a written report completed indicating the subsequent treatment and resolution of the condition.

Procedures for Reporting Adverse Events:

All serious and Unanticipated Adverse Device Effects that are related or possibly related to participation will be reported to the Principal Investigator and the sponsor within 24 hours of the investigator becoming aware of the event. The Principal Investigator will report the event

to the Institutional Review Board (IRB) as soon as possible, but in no event later than 10 working days after the investigator first learns of the event (21 CFR 812.150(a)(1)). All fatal or life-threatening events will be reported immediately to the IRB.

The CRO/Sponsor will immediately conduct an evaluation of an UADE and will report the results of the evaluation to FDA, all reviewing IRBs, and participating investigators within 10 working days after the sponsor first receives notice of the effect (21 CFR 812.46(b), 812.150(b)(1)).

All adverse events—including non-serious adverse events that are not related to the device—will be documented and submitted by the investigator on the Adverse Event Form. In the final clinical report for this study all adverse events, regardless of classification (i.e. non-device related, serious, significant, and non-significant), will be reported.

Medical Monitor Responsibilities:

The Medical Monitor will be a physician specializing in optometry or ophthalmology. To reduce study bias concerns, the Medical Monitor will not have any real or potential conflict of interest with the Sponsor, Study Investigator or participating Investigative site.

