	
1) central or paracentral location;
 
2) penetration of Bowman's membrane;
 
3) infiltrate > 2 mm diameter;
 
4) associated with iritis ≥ grade 2;
 
5) associated with any increase in intraocular pressure;
 
6) culture positive for microorganisms;
 
7) increasing size or severity at subsequent visits.
 
b) Any central or paracentral corneal event (such as vascularization) that results in permanent opacification.
 
c) Any serious adverse ophthalmic events including hypopyon and hyphema.
 
d) Any neovascularization within the central 6 mm of the cornea.
 
e) The loss of two or more lines of visual acuity that fail to resolve.
 
f) All cases of iritis.
	
Significant but non-serious adverse events	Significant but non-serious AEs should include, but not be limited to: 
 — peripheral non-progressive non-infectious ulcers; — all symptomatic corneal infiltrative events; — all cases of corneal staining greater than or equal to grade 3; — a temporary loss of ten or more letters of best spectacle corrected visual acuity (for greater than or equal to 2 weeks); — cases greater than or equal to grade 2 neovascularization; — any ocular event that necessitates temporary lens discontinuation of greater than or equal to 2 weeks; — lens adhesion or lens binding to the cornea; — significantly distorted corneal topography (significant distortion of keratometry mires or aberrant findings in corneal topography); — any ocular AE that requires the practitioner's intervention, including medication (not including minimal lubrication). 	Notify sponsor as soon as possible, no later than 10 business days ; IRB and FDA reporting as per requirements
Unanticipated Adverse Device Effects (UADE)	Unanticipated adverse device effect means any serious adverse effect on health or safety or any life-threatening problem or sight-threatening, or death caused by, or associated with, a device, if that effect, problem, or death was not previously identified in nature, severity, or degree of incidence in the investigational plan or application (including a supplementary plan or application), or any other unanticipated serious problem associated with a device that relates to the rights, safety, or welfare of subjects.	Notify sponsor and IRB as soon as possible, but no later than 10 business days, if events that are fatal or life threatening, report immediately ; IRB and FDA

		reporting as per requirements

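### Section 14 and the Adverse Event Form set different sponsor-notification limits in two of three event classes, and the form carries a probably misplaced deviation instruction

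*Combined protocol and SAP*

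**What the plan says.** Section 14 has a classification table with a reporting column. The Adverse Event Form in Appendix 3 carries a near-identical table.

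- **Serious adverse events.** Both tables give the sponsor limit as 24 hours.
- **Significant non-serious adverse events.** Section 14: "Notify sponsor as soon as possible, within 5 working days". Form: "Notify sponsor as soon as possible, no later than 10 business days".
- **UADEs.** Section 14 table: "Notify sponsor immediately". Section 14, Procedures for Reporting Adverse Events, sends serious and unanticipated device effects that are related or possibly related to the "sponsor within 24 hours of the investigator becoming aware of the event". Form: "Notify sponsor and IRB as soon as possible, but no later than 10 business days", with immediate reporting only for fatal or life-threatening events.

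Two further clocks in Section 14 matter. The IRB must hear "in no event later than 10 working days after the investigator first learns of the event". The sponsor's own evaluation of a UADE is due "within 10 working days after the sponsor first receives notice of the effect".

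Later on the same form, the question whether the subject continued in the study is followed by an instruction to complete a Protocol Deviation Report if the answer is yes.

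**The concern.** Section 14, Procedures for Handling Adverse Events, requires the form for each adverse event, so it is the text in front of site staff when they classify an event. Nothing states that Section 14 overrides it. A site that follows the form in good faith can therefore miss a Section 14 limit. For a UADE the effect can carry forward, because the sponsor's evaluation clock starts only when the sponsor receives notice.

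The deviation line is a smaller matter of the same kind. Followed literally, it creates a deviation record for every subject who has an adverse event and stays in the study. Section 6.4.8 asks for written justification to use data from a subject with a deviation, and Section 7 ties the per-protocol set to adherence.

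**Working it through.** No sample size, power or error rate is involved. The check sets the texts side by side.

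| Event class | Section 14, sponsor limit | Adverse Event Form, sponsor limit | Agree? |
|---|---|---|---|
| Serious | 24 hours | 24 hours | Yes |
| Significant non-serious | 5 working days | 10 business days | No |
| UADE, not fatal or life-threatening | Immediately (table); 24 hours from awareness if related or possibly related (reporting procedures) | 10 business days | No |

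Three classes compared, one agrees, two differ.

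**Size of the differences at the outer limits** (counted from a weekday, no public holidays, the form's clock taken to start at investigator awareness because the form states no start):

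- Significant non-serious: 10 / 5 = 2, so the limit doubles. In calendar days, 14 − 7 = 7 more. No later clock in the documents depends on these days.
- UADE, sponsor notice: 10 business days = 14 calendar days, against 1 day under the 24-hour rule. 14 − 1 = 13 calendar days.
- UADE, IRB notice: 10 working days in Section 14, 10 business days on the form. No difference.

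The form's UADE figure equals Section 14's IRB limit. An IRB limit may have been carried into the sponsor wording, but that is an inference.

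**Events that are both serious and UADEs.** The form asks about the two attributes in separate yes/no items, so both can be yes. Its table then gives 24 hours and 10 business days for one event. In Section 14 the reporting procedures put both kinds in one sentence with one 24-hour sponsor limit, which largely settles the matter. What remains there is the small difference between immediately and 24 hours. The two-limit problem is thus essentially confined to the form.

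**The deviation instruction.** Three places on the forms can be compared:

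1. Follow-up form: the same instruction stands under the question whether there was any protocol deviation, where it makes sense.
2. Adverse Event Form: it stands under the question whether the subject continued.
3. Protocol Deviation Report: the question about continuing appears again, with no such instruction.

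Section 10 neither defines nor lists continuing after an adverse event as a deviation. The line on the Adverse Event Form is therefore probably misplaced. The number of subjects affected cannot be computed, because the documents give no adverse event rate.

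**The case against.** The strongest reply is that little delay would follow in practice. A site that meets the shorter limit satisfies both texts, and Section 8 calls the Appendix 3 forms samples. Several other routes exist:

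- Section 14 has serious or severe sight-threatening events "promptly communicated by telephone to CRO, the Medical Monitor, and to the IRB".
- Cases that need culturing go to the Medical Monitor and CRO on the same business day.
- The form's serious-event row gives 24 hours, and its serious-event question asks for a report to the IRB and CRO as soon as possible.
- Section 6.5 provides ongoing remote monitoring by the CRO.

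A UADE is largely defined by seriousness, so most would meet one of these routes. All of this stands and limits the risk. It does not remove the conflict: the telephone and culture routes do not name the sponsor, they do not cover significant non-serious events as a class, and no text ranks the form below Section 14.

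A reader might infer more than the documents support:

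- **That a UADE evaluation would typically arrive at 28 days.** Adding the form's 10 business days to the sponsor's 10 working days gives 20 working days, or 28 calendar days, against 14 to 15 under the 24-hour rule. That needs a UADE outside the ocular serious-event definition, not fatal or life-threatening, with both limits fully used and the as-soon-as-possible wording ignored. It is an unlikely upper bound.
- **That nothing governs an event that is both serious and a UADE.** Section 14's reporting procedures largely do.
- **That differing start points make serious-event limits lapse before a visit.** The limit that runs from occurrence concerns written confirmation of the telephone report, a different act with different recipients. Nominal visit gaps are 7, 7, 16, 30 and 31 days. Two equal the 7 calendar days of that limit rather than exceed it, and the calculation ignores visit windows and interim visits.
- **That subjects would drop out of the analysis through false deviations.** Section 6.4.8 withholds evaluability only for a significant deviation, the Clinical Monitor reviews compliance under Section 10, and Section 7 keeps all enrolled subjects for safety reporting.

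**Conclusion.** The inconsistency is real, is in current text, and covers two of three event classes. The outer limit doubles from 5 to 10 working days for significant non-serious events. For UADEs that are not fatal or life-threatening it moves from immediately or 24 hours to 10 business days. A site following the form could notify the sponsor later than Section 14 permits, and for a UADE the sponsor's evaluation could start later in consequence. The deviation instruction is probably misplaced and, taken literally, produces false deviation records.

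The severity is minor. Serious-event limits agree, initial IRB notice of a UADE is no later under the form, and Section 14 has every adverse event reported in the final clinical report whatever its class. No endpoint, estimate or adverse event count changes. The calendar-day figures rest on weekday awareness, no public holidays, and a form clock that starts at awareness.

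**What to change.** The sponsor should reconcile Section 14 (classification table and reporting procedures) with the table on the Adverse Event Form, so that each class has one sponsor-notification limit, the same in both places. The choice of limit is the sponsor's. For an event that is both serious and a UADE, the form should be made consistent with Section 14's reporting procedures. The deviation instruction under the question about continuing in the study should be removed or corrected. Section 10 needs no change.

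The cost is an amendment to text and form. Section 9 requires IRB approval and training of investigators and coordinators before implementation, plus an IDE supplement or, if the change counts as minor, a note-to-file. No new data, visits or subjects are needed.

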7. STATISTICAL CONSIDERATIONS

The CRO will manage data analysis and reporting. Subject characteristics and study conduct summaries will be reported—including tables such as a subject disposition table, demographics and baseline characteristics tables (including age, gender, baseline refraction, lens wear experience), summary table of screen failures by reason, accountability of eyes enrolled, and subjects excluded from key analysis sets.

All descriptive summary statistics will be displayed with n and % for categorical data, and with mean, standard deviation, median, minimum, and maximum for continuous data. The unit will be eye. Tables will be presented by treatment and overall. Slit lamp findings will be presented by all study visits, tabulated by eyes and incidence rate for completed test lens group, completed control lens group, discontinued test lens group and discontinued control eyes group. Primary and secondary outcomes will be analyzed by descriptive statistics only. As such, there are no statistical hypotheses to be tested.

Trend analysis profile will be provided following directions provided in the FDA guidance *Premarket Notification [510(k)] Guidance Document for Class II Daily Wear Contact Lenses*. All participants who meet the eligibility criteria, adhere to the protocol, and successfully complete the full study assessment will be available for the per-protocol analysis. Subjects with missing data will be included in the analysis unless there is some non-response-related reason to exclude them, such as a protocol violation/invalid data. Data from all enrolled subjects will be used for reporting of adverse events or other safety related outcomes.

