Investigator Printed name of the signer _____

Signature _____

Adverse Event Form

CONFIDENTIAL

84

Adverse Event Form

Subject ID: _____

Date: _____ (MM/DD/ YYYY)

Time: _____ (HH:MM, 24h)

Principal Investigator: _____

Clinical Investigator: _____

Indicate Visit: Baseline / Day 7 / Day 14 / Day 30 / Day 60 / Day 91 /
 Other (please explain the time in investigation from dispensing _____)

Date of Dispensing: _____

Type of Report: Initial AE AE Follow-up (Number of Days following the initial AE Visit: _____)

Adverse events should be differentiated into device related and non-device related. Any corneal infiltrate, ulcer, neovascularization, etc. shall be presumed to be device related unless the case history clearly indicates some other origin. All corneal ulcers shall be recorded in the study report.

Type of Adverse Event: _____

Classification	Definition and condition	Reporting
Serious Adverse Events (SAE)	
Serious Adverse Device Events are those events that result in, or have potential to cause, either permanent impairment of an ocular function or damage to an ocular structure, and may necessitate medical or surgical intervention.
 
Serious AEs may include any hazardous, sight-threatening conditions occurring after exposure to test article, including but not limited to the following.
 
a) A presumed infectious ulcer (defined as a progressive erosion of the corneal tissue). Signs may include irregular focal infiltrates (> 1 mm); active lesions with raised edges; significant diffuse infiltration; anterior corneal to mid-stromal involvement; erosion with overlying staining; conjunctival and lid edema; anterior chamber reaction (iritis); severe bulbar and limbal redness. Symptoms associated with a presumed infectious ulcer (microbial keratitis) may include pain of rapid onset; severe redness; purulent or mucopurulent discharge; tearing; photophobia. For the purposes of reporting, a corneal ulcer which has any of the following characteristics should be considered in this category:
	
Notify sponsor as soon as possible, within 24 hrs; IRB and FDA reporting as per requirements

CONFIDENTIAL

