--	--	-------------------------------

Date of Occurrence: ____/____/_____(MM/DD/YYYY)

Date First AE is Observed by Investigator: ____/____/_____(MM/DD/YYYY)

Date of Resolution: ____/____/_____(MM/DD/YYYY)

Duration of Event: _____ days

Eye Involved: OD / OS /OU

Clinical Observations

Describe event including slit lamp observation

Diagnosis: _____

List of Acuities at Visits (logMar VA)

	Uncorrected VA		Contact Lens Corrected VA		Best Corrected VA		Pinhole VA if needed	
	OD	OS	OD	OS	OD	OS	OD	OS
Baseline								
Beginning of Event								
Poorest Acuity during Event								
At Resolution or Final Visit Seen								

Severity: _____ 1 = Mild 2 = Moderate 3 = Severe 4 = Life-Threatening

If applicable, were images captured for documentation of the AE? Yes No

AE Treatment: select all that applies

- 0 = None
- 1 = Study device replacement/modification
- 2 = Medical intervention
- 3 = Culturing
- 4 = Study device discontinued for _____ time period
- 5 = Hospitalization
- 6 = Other

Describe details including relevant tests/laboratory data with dates

Outcome of AE / Resolution Status:

- 0 = Resolved without sequelae
- 1 = Recovered with minor impairment / sequelae
- 2 = Recovered with major impairment / sequelae
- 3 = Ongoing/Continuing treatment without sequelae
- 4 = Ongoing/Continuing treatment with sequelae
- 5 = Condition worsening
- 6 = Death
- 7 = Unknown
- 8 = Other

Describe details including relevant tests/laboratory data with dates

Other Relevant History, including Preexisting Medical Conditions

Describe

--

Study Device Relationship: 0 = Unrelated (clearly not related to the study device)
1 = Unlikely related (doubtfully related to the study device)
2 = Possibly related (may be related to the study device)
3 = Probably related (likely related to the study device)
4 = Definitely related (clearly related to the study device)

Describe details

--

Is this Ocular event? Yes No

Is this an Unanticipated Adverse Effect? Yes No

Is this a Serious Adverse Event? Yes No

(If yes, complete paper SAE form and report to IRB and CRO as soon as possible)

Is this Significant but non-serious Adverse Event? Yes No

Did Subject Continue in Study? Yes No

(If Yes, fill out the Protocol Deviation Report and contact to CRO accordingly)

Reportable to CRO/Sponsor? Yes No **When?** ____/____/_____(MM/DD/ YYYY)

Reportable to IRB/FDA? Yes No **When?** ____/____/_____(MM/DD/ YYYY)

I am accepting the data pertaining to this subject to be complete and accurate.

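### The sample Adverse Event Form accepts a both-eyes (OU) entry with single severity, outcome, relatedness and date fields, although Section 14 counts and documents each eye separately

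*Combined protocol and SAP*

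**What the plan says.** Section 14, under the procedures for handling adverse events, sets two rules. The first concerns forms: "An Adverse Event Form will be completed for each adverse event". The second concerns laterality: "If both eyes are involved, each eye will be counted as one adverse event and Adverse Event information will be completed" for each eye. Read together, a bilateral event needs two Adverse Event Forms.

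Section 7 fixes the unit of analysis: "The unit will be eye". Section 6.1.3 lists ocular adverse events first among the primary outcomes, and Section 7 limits the analysis to descriptive statistics, with no hypothesis test.

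The Adverse Event Form in Appendix 3 has a single laterality field, "Eye Involved: OD / OS /OU". Severity is one entry per form, "Severity: _____ 1 = Mild 2 = Moderate 3 = Severe 4 = Life-Threatening", and the same holds for occurrence date, resolution date, duration, treatment, outcome and device relationship. Only the acuity table has separate columns for the right and left eye. One form serves both first and later reports ("Type of Report: Initial AE AE Follow-up"). No event number is printed on it. Section 8 describes Appendix 3 as a sample of the case report forms.

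**The concern.** Under Section 14, OU should not be a valid entry for an ocular event, yet the form invites it and nowhere tells the site to open a second form. A site that follows the form's own layout can depart from the protocol's counting rule without noticing.

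Two things are at stake. One is information: a single OU record holds one severity grade, one outcome, one relatedness score and one resolution date, so a difference between the eyes has no structured place. The other is the count. The analysis is descriptive, so the tabulated event counts and rates are themselves the safety result that goes into the submission. If some bilateral events are one record and others are two, the numerator depends on how the form was completed unless the analyst corrects for it.

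**Working it through.** The plan states no adverse event rate, bilateral share or expected count, so there is no figure to reproduce. The check is a comparison of texts, followed by illustrative arithmetic.

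**Rule against form**

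| Item | Section 14 | Sample Adverse Event Form |
|---|---|---|
| Records for a bilateral event | Two, one per eye | One is possible, marked OU |
| Severity, treatment, outcome, device relationship | Completed for each eye | One field each |
| Occurrence and resolution dates | Completed for each eye | One field each |
| Acuity | Completed for each eye | Split right and left |
| Instruction to file one form per eye | Follows from the rule | None printed |

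The form agrees with the rule on acuity only.

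**Size of the possible miscount**

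Assumptions: S affected subjects, one event episode each, a share b of episodes bilateral, and every bilateral episode entered once as OU.

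- Section 14 count: S(1 − b) + 2Sb = S(1 + b)
- Count of forms: S
- Shortfall: [S(1 + b) − S] / [S(1 + b)] = b/(1 + b)

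| Assumed b | Form count ÷ Section 14 count | Shortfall |
|---|---|---|
| 0% | 1.000 | 0% |
| 10% | 0.909 | 9.1% |
| 25% | 0.800 | 20.0% |
| 50% | 0.667 | 33.3% |
| 100% | 0.500 | 50.0% |

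Example at full enrolment (Section 6.3.6: up to 50 test and 25 control subjects, so 50 × 2 = 100 and 25 × 2 = 50 eyes). Suppose six test subjects are affected, three of them in both eyes. Section 14 gives 6 + 3 = 9 events, or 9 per 100 eyes. The form count gives 6, or 6 per 100 eyes. One bilateral event in the control arm is 2/50 = 4% by the rule and 1/50 = 2% by form count.

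An error in the other direction is also possible. If a site files two forms for a bilateral event, marks both OU, and each is then split into two eyes, the count becomes S(1 − b) + 4Sb = S(1 + 3b). Relative to S(1 + b), that is 1.4 at b = 25% and 2.0 at b = 100%.

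**The case against.** The strongest reply is that the governing rule is already written. Section 14 asks for a form per event and counts each eye, and Section 7 makes the eye the unit. OU means both eyes, so an analyst who applies those sections counts the record as two. The undercount then arises only if the protocol's own rule is ignored. This stands: the shortfall in the table is conditional, and a reader should not infer that the count is necessarily halved. Section 4.2 adds that infections, at least, almost always affect one eye, which points to a small b for that kind of event.

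It can also be said that eye-level detail is not wholly lost. The form has free-text descriptions, the Follow Up Visit Form grades slit-lamp findings by eye, and the Medical Monitor reviews serious and device-related events. This stands in part. Those sources can help to reconstruct clinical severity, but they hold no eye-specific relatedness score, outcome code or resolution date.

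Three stronger readings are tempting, and the documents do not support them.

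- A reader might infer that follow-up reports cannot be tied to their event because no event number is printed. The form does carry subject ID, report type, days since the initial event visit, occurrence date, eye and diagnosis, which separate most concurrent events. Appendix 3 is also only a sample, and the live eCRF may number its records.
- A reader might infer that non-ocular events cannot be told apart. A separate yes/no item on the same form asks whether the event is ocular. What is missing is only an N/A choice in the eye field.
- A reader might infer that sites will record bilateral events differently. That is a risk, and nothing in the documents shows it happening.

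**Conclusion.** The point holds as a mismatch between form and rule on a primary outcome. A single OU entry satisfies the sample form and breaks Section 14. The firm consequence is that severity, outcome, relatedness and resolution date are not captured by eye in their designated fields when the two eyes differ. The conditional consequence is an undercount of b/(1 + b), from 0% to 50% over the full range of b, if forms are tallied without applying Section 14. These figures rest on an assumed bilateral share, one episode per affected subject, and every bilateral episode being entered once as OU.

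The effect is on descriptive counts and rates. No test, power or sample size calculation is touched. The missing event number is secondary. The change is worth making because it is cheap and is best done before data entry begins.

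**What to change.** - On the Adverse Event Form, remove OU for ocular events so that each affected eye has its own record, marked OD or OS. Add N/A to the eye field for non-ocular events.
- State in Section 7 that ocular adverse events are counted by eye, from initial reports only.
- If the live eCRF does not already number records, add an event number that follow-up reports must carry and that links the two eyes of a bilateral event.

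The cost is a few field edits on one eCRF, a sentence in Section 7, and a second short form for each bilateral event.
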